5.4.1. Re-screening

Individuals who do not meet the criteria for participation in this study (screen failure) may be rescreened once, including if a positive SARS-CoV-2 test results is obtained. Rescreened participants should be assigned a new participant number.

5.4.2. Re-testing of Clinical Laboratory Values during Screening

If a participant fails any of the laboratory criteria, the test may be repeated once within the screening period. If the participant fails the laboratory criteria for a second time they will be considered a screen failure. The urine drug screen can only be repeated for a valid reason (e.g. false positive result due to medication use, poppy seed consumption).

If a blood sample needs to be repeated due to sample handling problems, breakage or sample integrity, this is not considered a re-testing. Further details regarding the procedure for re-testing may be found in the Study Reference Manual (SRM).

6. STUDY INTERVENTION

Study intervention is defined as any investigational intervention or placebo intended to be administered to a study participant according to the study protocol.

6.1. Study Intervention(s) Administered

ARM Name	Active	Placebo
Intervention Name	GSK3858279	Placebo
Type	Biologic	Placebo
Dose Formulation	Solution for injection. GSK3858279 is formulated in 0.79 mg/mL sodium acetate, 50 mg/mL Sorbitol, 0.4 mg/mL polysorbate 20, glacial acetic acid 0.28 mg/mL, water for injection, pH 5.0. GSK3858279 contains no preservative.	Solution for injection. Normal Saline (0.9% sodium chloride)
Unit Dose Strength	50 mg/mL. Each vial has an extractable volume of 3.0 mL (150 mg per vial).	0.9% w/v sodium chloride, placebo level variable.
Dosage Levels	3 mg/kg. Single dose, once per study period.	Single dose, once per study period.
Route of Administration	IV Infusion	IV Infusion
Dosing Instructions	GSK3858279 will be infused over 1 hour. GSK3858279 can be diluted in normal saline prior to administration	The appropriate volume of placebo will be infused over 1 hour.
Use	Experimental	Placebo-control
IMP and NIMP	IMP	Placebo
Sourcing	Study medication is supplied by GSK.	Provided locally by the trial site, subsidiary, or designee.

Packaging and Labelling	Bulk supplies will be provided in a vial contained within a carton. Each vial and carton will be labelled as required per country requirement. Dispensed medication will be labelled as required per country requirement.	Commercial presentation. Dispensed placebo will be labelled as required per country requirement.
--------------------------------	---	--

6.2. Preparation/Handling/Storage/Accountability

- The investigator or designee must confirm appropriate temperature conditions have been maintained during transit for all study intervention received and any discrepancies are reported and resolved before use of the study intervention.
- Only participants enrolled in the study may receive study intervention and only authorized site staff may supply or administer study intervention. All study interventions must be stored in a secure, environmentally controlled, and monitored (manual or automated) area in accordance with the labelled storage conditions with access limited to the investigator and authorized site staff.
- The investigator, institution, or the head of the medical institution (where applicable) is responsible for study intervention accountability, reconciliation, and record maintenance (i.e., receipt, reconciliation, and final disposition records).
- Further guidance and information for the final disposition of unused study intervention are provided in the Pharmacy Manual.
- Under normal conditions of handling and administration, study intervention is not expected to pose significant safety risks to site staff. Take adequate precautions to avoid direct eye or skin contact and the generation of aerosols or mists. In the case of unintentional occupational exposure notify the monitor, Medical Monitor and/or GSK study contact.
- A Material Safety Data Sheet (MSDS)/equivalent document describing occupational hazards and recommended handling precautions either will be provided to the investigator, where this is required by local laws, or is available upon request from GSK.

6.3. Measures to Minimize Bias: Randomization and Blinding

6.3.1. Randomization

At Screening a unique Participant Number (case report form [CRF] number) will be assigned to any participant who has at least one Screening procedure performed, other than informed consent. The unique Participant Number will be used to identify individual participants during the course of the study.

Participants who meet the screening eligibility criteria will be randomized to a treatment group through RAMOS NG. The randomization is centrally controlled by RAMOS NG.

RAMOS NG will confirm the participants CRF number (Participant number) and provide the randomization number, where:

- A randomization number will be assigned from a randomization schedule generated by Clinical Statistics, prior to the start of the study, using validated internal software. Once assigned, this number must not be reassigned to any other participant in the study.

In each period participants will receive either GSK3858279 or placebo in a 1:1 ratio where the intervention codes are as follows:

Intervention code	Intervention Description
A	3 mg/kg IV GSK3858279
P	Placebo

During the trial, participants will receive both treatments, either two doses of GSK3858279 and one dose of placebo, or two doses of placebo and one dose of GSK3858279 with equal likelihood, the order of treatment assignments will be randomized. The exact sequences will be blinded to the blinded investigator site staff and participants to prevent bias. Participants will be randomized to a specific sequence on Day 1 of the first study period.

The randomization will be stratified based on whether the pain assessments will be performed in the morning or afternoon.

6.3.2. Blinding

This will be a double-blind study with respect to allocation of GSK3858279 or placebo to participants and the following will apply.

- The investigator or treating physician may unblind a participant's intervention assignment **only in the case of an emergency** OR in the event of a serious medical condition when knowledge of the study intervention is essential for the appropriate clinical management or welfare of the participant as judged by the investigator.
- The interactive voice response system (IVRS)/ interactive web recognition system (IWRS) will be programmed with blind-breaking instructions. In case of an emergency, the investigator has the sole responsibility for determining if unblinding of a participant's intervention assignment is warranted. Participant safety must always be the first consideration in making such a determination. If the investigator decides that unblinding is warranted, the investigator should make every effort to contact GSK prior to unblinding a participant's intervention assignment unless this could delay emergency treatment of the participant. If a participant's intervention assignment is unblinded GSK must be notified within 24 hours after breaking the blind. The date and reason that the blind was broken must be recorded in the source documentation and CRF, as applicable.

- If GSK personnel are not contacted before the unblinding, the investigator must notify GSK as soon as possible after unblinding, but without revealing the intervention assignment of the unblinded participant, unless that information is important for the safety of participants currently in the study.
- The date and reason for the unblinding must be fully documented in the CRF
- A participant will be withdrawn if the participant's intervention code is unblinded by the investigator or treating physician. The primary reason for discontinuation (the event or condition which led to the unblinding) will be recorded in the CRF. The participant will be followed up for safety monitoring if treatment was received.
- GSK's Safety and Medical Governance (SMG) staff may unblind the intervention assignment for any participant with an SAE. If the SAE requires that an expedited regulatory report be sent to one or more regulatory agencies, a copy of the report, identifying the participant's intervention assignment, may be sent to investigators in accordance with local regulations and/or GSK policy.
- There will be an unblinded site pharmacist to prepare the study intervention; however, they will not have contact with study participants.
- There may be two interim analyses performed (see Section 9.5 for details). Unblinded data will be reviewed by members of the GSK3858279 team who do not have direct contact with the study site or participants.

6.4. Study Intervention Compliance

- When the individual dose for a participant is prepared from a bulk supply, the preparation of the dose will be confirmed by a second member of the study site staff.
- Participants will receive study intervention at the clinical unit directly from the investigator or designee, under medical supervision, via IV route. The date and time of each dose administered in the clinic will be recorded in the source documents. The dose of study intervention and study participant identification will be confirmed at the time of dosing by a member of the study site staff other than the person administering the study intervention.

6.5. Concomitant Therapy

Any medication or vaccine (including over-the-counter or prescription medicines, vitamins, and/or herbal supplements) that the participant is receiving at the time of enrolment or receives during the study must be recorded along with:

- reason for use
- dates of administration including start and end dates
- dosage information including dose and frequency

The Medical Monitor should be contacted if there are any questions regarding concomitant or prior therapy.

Participants must abstain from taking prescription or non-prescription drugs (including vitamins and dietary or herbal supplements) within 7 days (or 14 days if the drug is a

potential enzyme inducer) or 5 half-lives (whichever is longer) before the start of study intervention until completion of the follow-up visit, unless, in the opinion of the investigator and sponsor, the medication will not interfere with the study.

6.5.1. Permitted Therapies

Paracetamol at doses of ≤ 3 grams/day, is permitted for use at any time during the study except those times referred to in Section 6.5.2.

Ibuprofen at doses of ≤ 1.2 grams/day, is permitted for use at any time during the study except those times referred to in Section 6.5.2.

6.5.2. Prohibited Medications

The following restrictions apply from first dose up until the 8-week follow-up visit

Medication	Pre-dose restriction	Other times
Ibuprofen	2 days	For 2 days prior to admission to unit and PainCart assessment (applicable from screening and during study)
Paracetamol	2 days	For 2 days prior to admission to unit and PainCart assessment (applicable from screening and during study)
All other pain medication including topical	1 month	From screening to 8-week follow-up
Live vaccine(s)	1 month	Throughout and for five half-lives after last dose
Biologic agents (monoclonal antibodies, therapeutic proteins)	3 months or 5 half-lives (whichever is the longer)	Throughout
Antiplatelet or anticoagulant agents	7 days	Throughout
Immunosuppressants	3 months or 5 half-lives (whichever is the longer)	Throughout
Systemic corticosteroids (inhaled administration is allowed)	Parenteral: 3 months Oral: 1 month	Throughout

6.6. Dose Modification

No modification of the dose-level is planned on the study.

6.7. Intervention after the End of the Study

GSK will not provide treatment after the end of the study.

7. DISCONTINUATION OF STUDY INTERVENTION AND PARTICIPANT DISCONTINUATION/WITHDRAWAL

7.1. Study Stopping Criteria

Recruitment will be halted by the sponsor if any of the following occur in participants receiving GSK3858279:

- Two participants experience the same SAE that is considered related to GSK3858279
- Two participants experience the same significant clinical or significant laboratory abnormality that may plausibly relate to GSK3858279 (according to the clinical judgement of the investigator)
- Two participants present with unexplained and clinically significant mucocutaneous bleeding (according to the clinical judgement of the investigator and medical monitor) that is considered causally related to GSK3858279.

Recruitment may be resumed after appropriate positive review of safety findings by the Principal Investigator and GSK Medical Monitor and following approval to restart the study from the regulatory agency and ethics committee.

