4. STUDY DESIGN

4.1. Overall Design

This study will be a randomized, double-blind, placebo-controlled, three-period two-treatment incomplete-block crossover study in healthy participants to investigate the effects of IV GSK3858279 on evoked pain tests in the PainCart. The study will be performed in a single centre.

In each period, participants will receive either GSK3858279 or placebo in a 1:1 ratio. During the trial, participants will receive both treatments, either two doses of GSK3858279 and one dose of placebo, or two doses of placebo and one dose of GSK3858279 with equal likelihood. The order of treatment assignments will be randomized. (see Section 6.3).

A three period design has been chosen because there is a marked reduction in variability for estimating the direct and residual treatment effects in three-period designs compared to two-period designs even with a large proportion of missing values, the three-period design is far more efficient than the two-period design [Carriere, 1994].

The total duration of the study (from signing informed consent until final follow-up visit) for each participant will be approximately 6 months. Study participation may be prolonged in the event the study is on-hold. Screening period will be a maximum of 28 days prior to study procedures, each study period will be approximately 2 weeks with at least a 4-week wash-out period between dosing (i.e. Day 1) in each of the study periods, final follow-up visit will be at approximately 8 weeks after last dose.

Participants will arrive at the research unit either one or two days before dosing, for the non-UVB-MITT and UVB-MITT group respectively. After arrival, subjects will be tested for SARS-CoV-2. Urine will be screened for the presence of drugs and an alcohol breath test will be performed. For participants with a positive urine drug screen or alcohol breath test, the treatment occasion may be rescheduled at the discretion of the principal investigator and GSK medical monitor. UVB irradiation will be applied approximately 24 hours before dosing in the UVB-MITT population only. ECG and vital signs will also be performed.

Participants will be assigned to receive treatment and pain assessments during either morning or afternoon sessions. They will continue to receive treatment and pain assessments at approximately the same time of day throughout all three study periods.

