7.2. Discontinuation of Study Intervention

A participant will be permanently withdrawn from study treatment if any of the following symptoms or abnormalities occur, and an investigation will be carried out as described below. After withdrawal of treatment (under these conditions), where possible participants should complete the Early Withdrawal visit and be followed up for safety monitoring. Study medications will be discontinued and the participant withdrawn from the study in the event of any of the following:

[figure not shown]
- All serious infections
- Severe or serious hypersensitivity reactions, including anaphylaxis
- If the liver chemistry stopping criteria (Section 7.2.1) or QTc stopping criteria (Section 7.2.2) are met.
- Other serious or severe adverse events, at the discretion of the Investigator, after consultation with the GSK Medical Monitor.

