7.2.3. SARS-CoV-2 related stopping criteria

If a participant develops COVID-19 like symptoms during the course of the study, procedures as specified in CHDR SOP GGECOVID will be followed.

Withdrawal of participants from the study will be at the discretion of the Principal Investigator, but should first be discussed and agreed with the GSK Medical Monitor. Further dosing and study related procedures except those required for participant safety and well being should be paused until the discussion is complete.

Participants that test positive for a SARS-CoV-2 infection after the first study dose are withdrawn from the study (after discussion with the GSK Medical Monitor and PI) will be replaced at the discretion of the Sponsor and in consultation with the Principal Investigator.

Subjects with a SARS-CoV-2 infection will be followed-up according to SOP GGECOVID.

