8. STUDY ASSESSMENTS AND PROCEDURES

- Study procedures and their timing are summarized in the SoA.
- Protocol waivers or exemptions are not allowed.
- Immediate safety concerns should be discussed with the sponsor immediately upon occurrence or awareness to determine if the participant should continue or discontinue study intervention.
- Adherence to the study design requirements, including those specified in the SoA, is essential and required for study conduct.
- All screening evaluations must be completed and reviewed to confirm that potential participants meet all eligibility criteria. The investigator will maintain a screening

log to record details of all participants screened and to confirm eligibility or record reasons for screening failure, as applicable.

- Procedures conducted as part of the participant's routine clinical management (e.g., blood count) and obtained before signing of ICF may be utilized for screening or baseline purposes provided the procedure met the protocol-specified criteria and was performed within the time frame defined in the SoA.
 - The maximum amount of blood collected from each participant over the duration of the study, including any extra assessments that may be required, will not exceed 500 mL.
 - Repeat or unscheduled samples may be taken for safety reasons or for technical issues with the samples.

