10.1.9. Study and Site Start and Closure

The study start date is the date on which the clinical study will be open for recruitment of participants.

The first healthy participant to be screened is considered the first act of recruitment and will be the study start date.

GSK or its designee reserves the right to close the study site or terminate the study at any time for any reason at the sole discretion of GSK. Study sites will be closed upon study

completion. A study site is considered closed when all required documents and study supplies have been collected and a study-site closure visit has been performed.

The investigator may initiate study-site closure at any time, provided there is reasonable cause and sufficient notice is given in advance of the intended termination.

Reasons for the early closure of a study site by the sponsor or investigator may include but are not limited to:

- Failure of the investigator to comply with the protocol, the requirements of the IRB/IEC or local health authorities, the sponsor's procedures, or GCP guidelines
- Inadequate recruitment of participants by the investigator

If the study is prematurely terminated or suspended, the sponsor shall promptly inform the Investigators, the IECs/IRBs, the regulatory authorities, and any contract research organization(s) used in the study of the reason for termination or suspension, as specified by the applicable regulatory requirements. The Investigator shall promptly inform the subject and should assure appropriate subject therapy and/or follow-up.

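### Protocol 7.1 halts recruitment when a safety trigger is met but does not hold dosing in participants already randomised

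*Protocol*

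**What the plan says.** Protocol 7.1 (Study Stopping Criteria) lists three triggers, each requiring two participants on GSK3858279: the same related SAE, the same significant clinical or laboratory abnormality plausibly due to the drug, or unexplained mucocutaneous bleeding judged causally related. The action is "Recruitment will be halted by the sponsor if any of the following occur". Recruitment may then resume after the Principal Investigator and the Medical Monitor have reviewed the safety findings, and "following approval to restart the study from the regulatory agency and ethics committee".

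Protocol 4.1 adds that "Study participation may be prolonged in the event the study is on-hold", without saying what would put the study on hold or what happens to dosing if it is. It also sets the allocation: "In each period, participants will receive either GSK3858279 or placebo in a 1:1 ratio". The synopsis (1.1) states that there is no data monitoring committee or other committee.

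**The concern.** A recruitment halt protects people who have not yet entered, including replacements. It does not reach people who are already in. Here each participant is randomised once, on Day 1 of Period 1 (6.3.1), and then follows a fixed sequence of three infusions at least four weeks apart. Read literally, 7.1 would let scheduled infusions continue after two participants had the same drug-related SAE.

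These are healthy volunteers with no direct benefit (2.3.2). Repeat exposure is a real feature of the design: half the participants are due two active doses. The risk table in 2.3.1 describes infusion reactions in one monkey on Days 22 and 29 of weekly dosing. Section 4.4 puts unbound CCL17 at only about 30% of baseline four weeks after a dose. A predefined stopping rule exists so that the decision to dose again after such a signal is not left to case-by-case judgement.

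**Working it through.** The plan gives no figure on this point, so there is none to reproduce. The check compares every provision that could stop dosing, then counts the infusions that a recruitment halt does not reach.

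**Provisions compared**

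| Protocol section | What it does | Tied to the 7.1 triggers? | Stops dosing in all randomised participants? |
|---|---|---|---|
| 7.1 | Halts and resumes recruitment | Yes | Not stated |
| 7.2 | Withdraws the affected participant; its last item is "Other serious or severe adverse events, at the discretion of the Investigator, after consultation with the GSK Medical Monitor" | No | No, individual level |
| 7.2.3 | For COVID-19: "Further dosing and study related procedures except those required for participant safety and well being should be paused until the discussion is complete" | No | No, individual level |
| 7.3 | Allows withdrawal of a participant at the investigator's discretion | No | No, individual level |
| 8 | Safety concerns go to the sponsor "to determine if the participant should continue or discontinue study intervention" | No | No, one participant at a time |
| 10.1.9 | "GSK or its designee reserves the right to close the study site or terminate the study at any time for any reason" | No | Only if the sponsor so chooses |
| 4.1 | Mentions an on-hold state | No | No trigger or dosing consequence given |

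Part of the 7.2 list is a figure not shown in the text reviewed, but it sits under a sentence about withdrawing an individual participant, so it cannot supply a study-level hold. The SAP contains no safety stopping rule. Section 7.2.3 shows that the protocol names dosing where it means to pause it, though that clause concerns one participant.

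**Schedule arithmetic**

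Inputs: three periods, one infusion in each; at least 28 days between doses (synopsis, 4.1); 1:1 allocation in each period; at most 30 enrolled, about 24 completing (synopsis, 9.2).

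1. Dosing schedule left after a Period 1 dose: 2 intervals × at least 28 days = at least 56 days, with 2 infusions to come.
2. Planned active infusions = (N/2) × 3, of which (N/2) × 2 fall in Periods 2 and 3.
   - N = 30: 15 × 3 = 45 in total; 15 × 2 = 30 in Periods 2 and 3; 30/45 = 67%.
   - N = 24: 12 × 3 = 36 in total; 12 × 2 = 24 in Periods 2 and 3; 24/36 = 67%.
3. Cross-check against the sequences in SAP 5.1, N = 30: 15 on A/P/P contribute 15 × 1 = 15 active doses, all in Period 1; 15 on P/A/A contribute 15 × 2 = 30, all in Periods 2 and 3. The total is again 45. Every later active dose therefore belongs to the P/A/A half, and anyone given active drug in Period 1 has only placebo left.
4. Infusions still scheduled if a trigger is met when k participants (balanced by sequence) have had Period 1 and nothing later: 2k infusions, of which k are active.
   - k = 30: 60 infusions, 30 active.
   - k = 18: 36 infusions, 18 active.

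Once the last participant is randomised, a recruitment halt prevents no planned infusion except in replacements.

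**The case against.** The strongest reply is that this is loose drafting and the intent is clear. The section is titled as stopping the study, it opens the chapter on discontinuing the intervention, and approval to restart a study makes sense only if the study has stopped. The on-hold remark in 4.1 mainly concerns people already enrolled. Intent may well have been a full hold. But the restart wording is a condition on resuming recruitment, and neither phrase tells anyone to withhold an infusion.

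A second reply is that other safeguards exist. Withdrawal under 7.2 is mandatory for serious infections, severe or serious hypersensitivity, and the liver and QTc criteria. SAEs reach the sponsor within 24 hours (8.2.1). Section 10.1.1 allows changes that remove an immediate hazard to be made before ethics approval, and 10.1.9 covers suspension as well as termination. Regulator and ethics approval is needed before recruitment resumes. All of this stands, and a responsible sponsor would probably stop dosing. These routes either act on the affected individual or depend on a decision; none makes a hold follow from a 7.1 trigger.

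A third reply is that the two-thirds share holds for any three-period design with equal allocation, and that 30 active infusions is a ceiling. Both are right. The ceiling requires all 30 to have had Period 1 and none to have gone further, whereas with staggered entry fewer would remain. The later active doses also fall on only half the participants.

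Finally, SAP Amendment 1 (1.1, Version History) records that the study was terminated after the futility threshold was not met. The amendment may therefore have no effect on dosing in this trial, but that does not change whether the rule was adequate as written.

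**Conclusion.** The concern holds. Section 7.1 orders a recruitment halt only, and no provision in either document makes a dosing hold follow from its triggers. Up to 30 of 45 active infusions at N = 30 (24 of 36 at N = 24) lie beyond the reach of that halt once participants are randomised. These counts assume 1:1 allocation in each period and no dropout. They describe the schedule and say nothing about how likely a trigger is; the documents report no trigger event.

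The text should be changed. Confidence is medium because the surrounding wording suggests that a full hold was meant. If it was, the change makes the protocol say so; if it was not, the gap is one of substance.

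**What to change.** Amend two sentences in 7.1. In the first, make the halt cover recruitment and all further dosing of randomised participants, whatever their next assigned treatment, so that the hold does not reveal allocation. In the second, make the same review and approvals the condition for resuming both recruitment and dosing. State that safety follow-up of participants already dosed continues during the hold.

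The cost is a short protocol amendment. The drawback is that a hold could delay or lose some Period 2 and Period 3 PainCart data.
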